This study will provide us with information about the diagnostic quality of the nutritional screening carried out in our environment compared with the GLIM criteria for malnutrition. In addition, by comparing the prevalence of sarcopenia and the phase angle in patients with positive or negative screening, we will be able to estimate the risk of muscle and cellular dysfunction in patients with the worst clinical prognosis.

Methods

Trial design:

Cross-sectional single-center study comparing the diagnostic quality of the CIPA instrument in the diagnosis of malnutrition or risk of presenting it in hospitalized patients vs GLIM and subsequent prospective follow-up of patients for up to six months.

The aims:

Primary endpoint:

- Determine the diagnostic quality of the CIPA tool, in inpatients with stays longer than three days, in the observation of risk of malnutrition compared to the gold standard GLIM as a diagnosis of malnutrition.

Secondary endpoints:

- Determine the positive and negative predictive values in comparison to the selected gold standard.
- Determine the degree of reliability, likelihood ratio and diagnostic odds ratio of the tool compared to the gold standard.

- Determine the point of greatest balance between sensitivity and specificity for each of the three variables that make up the diagnostic instrument for malnutrition.
- Determine the degree of Kappa concordance between both diagnostic criteria (CIPA vs. GLIM).
- Establish the cut-off point for the phase angle of the population studied by bioimpedanciometry for men and women, and determine prognostic values according to the optimal cut-off point.
- Evaluate prognostic variables (mortality, average stay, readmission rate) according to the two tools under study (CIPA vs. GLIM) at discharge, together with early readmissions, and mortality at six months of prospective follow-up.
- Evaluate whether CIPA positive subjects obtain worse muscle functionality results according to dynamometry than CIPA negative subjects.
- Determine if there is a relationship between positive CIPA and sarcopenia according to established EWGSOP2 diagnostic criteria.
- Determine if there is a relationship between positive subjects with sarcopenia vs negatives in relation to the six-month prognosis.

Inclusion criteria:

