Adult subjects of both sexes with a hospital stay of more than three days and attached to one of the following departments: general surgery, internal medicine, vascular surgery, digestive system, hematology, nephrology, pulmonology, oncology, neurology, traumatology. The diagnostic evaluation of malnutrition and functionality will be carried out after three days of hospital stay, once the CIPA screening has been carried out.

Exclusion criteria:

Subjects who are not candidates for CIPA nutritional screening at the HUNSC are excluded: with a prognosis of hospital stay of less than or equal to three days; admission to services with a low incidence of malnutrition (ophthalmology, dermatology, obstetrics...); pediatric patient or critical care unit and palliative

care; patients already receiving artificial nutritional treatment. Patients with edemo-ascitic overload will also be excluded.

Written informed consent will be requested from patients who meet all the inclusion criteria and none of the exclusion criteria, and in the case of minors or handicapped, that of their parents or legal guardians will be collected.

Expected criteria for withdrawal of study subjects:

Of all the personal data that is registered, each participant in the study will have access rights for their knowledge, rectification of inaccurate or incomplete data and cancellation (ARCO Rights). Any participant who wishes to exercise their ARCO rights must contact the doctor/investigator responsible at the Study Hospital where said data was collected and submit the corresponding form.

Study variables (primary and secondary):

Variable	Data collection
Sex	Basal
Age	Basal
Weight	Basal
Height	Basal
BMI	Basal
Cause of admission	Basal
Type of admission (urgent)	Basal
Days of hospital stay	Follow-up
Comorbidity	Basal
Diabetes mellitus	Basal
Dinamometry	Basal

Grip strength	Basal
CIPA (variables associated with the performance of the test)	Basal
GLIM (variables associated with the performance of the test)	Basal
Bioimpedanciometry (phase angle)	Basal
Fat Free Mass Index	Basal
Appendiceal skeletal muscle mass index	Basal
Sarcopenia	Basal
Patients with nutritional treatment	Follow-up
Mortality (to six months)	Follow-up
Readmissions (to six months)	Follow-up

Data Collect

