Once the patient is selected and coded to ensure data protection, after three days of stay, according to the usual protocol, the risk of malnutrition will be studied with CIPA and, later, GLIM will be performed on these patients.

For the evaluation of cell function, the phase angle obtained by bioimpedanciometry (Aker BIA 101 Anniversary) will be used and observing the ratio between reactance/resistance between body cell mass and fat-free mass. Likewise, muscular functionality will be evaluated by dynamometry (using a Jamar dynamometer), taking the maximum value of between two measurements in the dominant arm with an interval of at least one minute between one and the other. In turn, the values under study will be collected and the the data collection notebook according to coding. The risk of sarcopenia will be determined according to values observed in dynamometry and bioimpedance measurement established in the 2019 European consensus on Sarcopenia according to the EWGSOP2 criteria: grip strength determined by dynamometry, positive in males if < 27 kg and in women if < 16 kg, muscle volume, determined by bioimpedance analysis, positive if appendicular skeletal muscle mass < 20 kg in men and < 15 kg in women.

All subjects with a positive test according to the CIPA instrument will be treated according to the usual protocol to correct possible malnutrition or risk thereof,

while subjects with a negative CIPA test but a positive GLIM will be studied and constantly monitored, taking the appropriate measures according to criteria. optional. Patients will be followed up during their hospital stay and 6 months after discharge, prospectively collecting variables for the study of prognostic factors (hospital stay, early readmission rate, mortality).

The study consists of a first cross-sectional part that will be completed once the data of the 490 subjects selected through probabilistic sampling has been collected. The second part of the study will consist of the prospective follow-up of the patients and the variables will be analyzed with prognostic criteria. In these cases, follow-up will end 6 months after discharge. Thus, the total estimated months to complete the study is estimated at 15 months. The study will be conducted entirely at HUNSC.

Difficulties and limitations of the study:

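### Grip strength is measured only in the dominant arm, with no rule for a paretic, injured or immobilised arm, although neurology and traumatology patients are eligible

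*Combined protocol and SAP*

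**What the plan says.** The Workplan sets the grip procedure as "taking the maximum value of between two measurements in the dominant arm with an interval of at least one minute" between readings, using a Jamar dynamometer. It then states the limits: "grip strength determined by dynamometry, positive in males if < 27 kg and in women if < 16 kg". The second component is muscle mass by bioimpedance, "positive if appendicular skeletal muscle mass < 20 kg in men and < 15 kg in women". On their joint use it says only this: "The risk of sarcopenia will be determined according to values observed in dynamometry and bioimpedance measurement". It does not say whether both components are needed.

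The Inclusion criteria list ten departments, among them "nephrology, pulmonology, oncology, neurology, traumatology". The Exclusion criteria remove patients who are not candidates for CIPA screening: short expected stay, low-incidence services, paediatric, critical or palliative care, and artificial nutrition already started. One study-specific exclusion is added: "Patients with edemo-ascitic overload will also be excluded". Nothing refers to the arms or to the ability to grip.

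Three secondary aims use the measurement: dynamometry by CIPA result, sarcopenia against six-month prognosis, and "Determine if there is a relationship between positive CIPA and sarcopenia according to established EWGSOP2 diagnostic criteria".

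**The concern.** Grip in one arm stands in for whole-body muscle strength only if that arm has no local problem. Two of the ten eligible departments are places where weakness, fracture or immobilisation of an arm can be expected in some patients. For them a low reading may reflect the arm and not the muscle status that the study wants to measure.

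The plan leaves three things that site staff might do. They might test the dominant arm anyway, and a local deficit can then count as low strength. They might skip the test, and the patient drops out of the dynamometry and sarcopenia analyses for a reason linked to the admission. Or they might use the other arm without saying so. The table under Study variables lists dynamometry and grip strength but no field for the arm tested, its condition or a reason for a missing value. Department is not listed either. Cause of admission and comorbidity are collected, but need not show which arm was affected. The problem may therefore not be recoverable at analysis.

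At stake are the sarcopenia prevalence in the title and abstract and the three secondary aims above.

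**Working it through.** The plan states no figure for this point, so there is none to reproduce. The check sets the provisions side by side and then illustrates the size.

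**1. Provisions.**
- Arm: dominant, no alternative (Workplan).
- Limits: 27/16 kg, no exception (Workplan).
- Eligible: neurology and traumatology (Inclusion criteria).
- Exclusion for an impaired arm: none (Exclusion criteria).
- Code for a test that cannot be done, missing-data rule or sensitivity analysis: none (Statistical analysis of the data).
- Mention as a limitation: none (Difficulties and limitations of the study; Discussion).

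**2. Inputs for the illustration.**
- N = 490 (Workplan).
- p = 33% probable and 22.5% confirmed sarcopenia, from a Spanish inpatient cohort cited in the Discussion.
- f, the share of patients with an affected dominant arm: not in the documents. Assumed 2-6%. This is what equal department sizes (2 × 490/10 = 98 patients) with 10-30% affected would give: 9.8 to 29.4 patients, and 9.8/490 = 2.0%, 29.4/490 = 6.0%.
- All affected patients read below the limit: assumed, an upper bound.
- q, the share of falsely low-grip patients who also have low muscle mass: assumed 10-40%.

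**3. Low grip.** Observed prevalence = p + f(1 − p), so the shift is f(1 − p).
- f = 2%: 0.02 × 0.67 = 1.3 points, 33% to 34.3%.
- f = 6%: 0.06 × 0.67 = 4.0 points, 33% to 37.0%.

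**4. Confirmed sarcopenia, if low grip and low muscle mass are both required.** Shift = f(1 − p)q.
- Low end: 0.02 × 0.67 × 0.10 = 0.1 points.
- High end: 0.06 × 0.67 × 0.40 = 1.6 points.

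**5. Scale.** 95% half-width = 1.96 × √(p(1 − p)/490).
- At 33%: 1.96 × √(0.33 × 0.67/490) = 4.2 points.
- At 22.5%: 1.96 × √(0.225 × 0.775/490) = 3.7 points.

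Both shifts lie within these half-widths over the assumed range.

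**6. Primary endpoint.** The GLIM items described in Background and Data Collect are weight loss, BMI, muscle mass, intake and inflammation. The CIPA items are intake, albumin and BMI or arm circumference. Grip enters neither, so sensitivity and specificity are unaffected.

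**The case against.** The strongest reply is that this is an unspecified detail, not a wrong rule. No section says that a patient who cannot grip is to be scored low, and sensible staff may leave the value blank. Mild weakness need not bring a reading below 27 or 16 kg. Every input behind the size, except 490 and the two cited prevalences, is assumed. The sampling is described only as probabilistic, the Discussion expects that surgical areas may be under-represented, and the 33% comes from a cohort of medical inpatients. The resulting shift is no larger than sampling error, and the primary endpoint is untouched. Cause of admission and comorbidity are recorded, and multivariate models with a confounding check are planned.

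Most of this stands as a limit on size and certainty. It does not remove the gap. The Workplan does give a positive instruction, dominant arm with fixed limits, which can misclassify when followed. Leaving the value blank is no better handled. A systematic error is not reduced by sample size or reflected in a confidence interval. The multivariate models are described for follow-up of CIPA-positive patients, and the affected side is not among the listed variables.

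A reader might infer two stronger things. One is that every patient with an affected arm will be counted as sarcopenic. The documents do not support this: the handling is not stated, not every reading would fall below the limit, and the rule combining grip with muscle mass is not given. The other is that the rule produces a spurious link between CIPA, sarcopenia and mortality. That would require affected patients to differ in CIPA positivity or prognosis. This is plausible, since a neurological deficit can reduce intake, but the documents give nothing from which to establish it.

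**Conclusion.** The point holds as a gap in the measurement rule. Applied as written to the eligible population, it can class a local arm problem as low muscle strength; if patients are skipped, the loss is related to diagnosis. The listed variables would not distinguish these cases. It bears on the dynamometry and sarcopenia secondary aims and on the prevalence in the title, not on CIPA-versus-GLIM accuracy.

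Its true size is unknown. The illustrative shifts of 1.3-4.0 points in low grip and 0.1-1.6 points in confirmed sarcopenia rest on an assumed 2-6% affected, all below the limit, and on 10-40% of those falsely classed having low muscle mass. They show a modest bias that is worth preventing because prevention is nearly free.

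**What to change.** Amend the Workplan as follows.
- When the dominant arm has a neurological deficit, injury or immobilisation, take the two measurements in the unaffected arm.
- Record the arm used and the reason in the data notebook.
- If neither arm can be tested, code grip as not assessable, not as low, and report the number of such patients by CIPA status. This does not remove the missing data, but it makes their number and pattern visible.

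Add to the Statistical analysis of the data a sensitivity analysis of the dynamometry and sarcopenia results without patients measured in the non-dominant arm. Present it beside the main result, because dropping those patients is itself selective.

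The cost is a short addition to the procedure, two notebook fields and one extra analysis, with the same device, staff and visit. The small downside is that a few readings from the other arm may not be fully comparable. If recruitment has begun, apply the rule to the remaining patients and use recorded cause of admission and comorbidity to identify likely affected patients among those already measured.

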For the cross-sectional study of the quality of diagnostic criteria between the CIPA instrument and the current gold standard GLIM, a study of sensitivity, specificity, positive and negative predictive values, as well as the likelihood and an estimator of a single value such as the diagnostic odds ratio. In addition, they will determine the best equilibrium points for the three items of the CIPA instrument according to the Youden model, determining in each case the area under the curve (AUC). Likewise, the concordance between both CIPA tests and the GLIM gold standard will be determined by the Kappa coefficient according to Cohen's model. All point estimates will be accompanied by 95% confidence intervals.

For the follow-up study with CIPA positive patients, an initial univariate study of the factors that could determine prognostic levels in the patients will be carried out. These analyzes will be parametric/non-parametric according to the homoscedasticity and normality of the data in each distribution, analyzed by the Kolmogorov-Smirnov test. Subsequently, for the variables with statistical significance or clinical relevance found in the univariate analysis, multivariate models will be carried out with the aim of knowing the one that best fits the data and determining the prognostic factors in the patients studied. The selection of the final model will be guided by the principle of parsimony. Collinearity will be evaluated by the main regression component of the explanatory variables. While

the different models will be compared by the likelihood ratio and the Wald test. The existence of confusion will be evaluated by clinical criteria with a significant change of 10% over the coefficient obtained according to the variables included in the model. The model will be validated by the Hosmer-Lemeshow calibration test and by the area under the curve (AUC) as a measure of discrimination.

Workplan:

This study will select patients with an expected hospital stay of more than three days, through probabilistic sampling to control possible biases in the selection of subjects. The selection will be made in the departments specified by physicians or personnel trained for this purpose, establishing whether they meet all the established inclusion criteria and none of the exclusion criteria, according to the study protocol. Each patient will receive a full explanation of the study objectives and an informed consent form will be signed.

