The study of HM is an important objective since it has a high prevalence and is associated with a worse clinical prognosis, as well as higher healthcare costs. In addition, it has been shown that early treatment can mitigate these deleterious effects on the patient's health.

However, in clinical practice, the establishment of a hospital nutritional screening is complex. The lack of care time and the complexity of the same associated with nutritional therapy make its implementation very difficult, so carrying out a subsequent nutritional assessment is even more complicated unless there is enough specialized personnel.

The low cost of oral nutritional support in hospitalized patients and the scarcity of adverse effects if it is prescribed and taken properly, causes that in most hospitals a nutritional therapeutic tool is prescribed directly when the screening is positive without further evaluation. to confirm malnutrition.

The creation of the GLIM consensus [12] as a new definition of malnutrition has stimulated the comparison of previous screening or nutritional assessment methods (such as the VGS, MST, MUST or NRS-2002). Therefore, the objective of this work is to carry out this analysis with the CIPA nutritional screening, designed, validated and implemented in our environment. CIPA screening meets criteria that have made it the choice for its implementation, such as: it uses tools that are commonly used in clinical practice, it does not require specialized personnel, it is performed quickly and at low cost, being useful for detection of malnourished patients or at risk of malnutrition, predicting their prognostic evolution.

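### Routine nutritional treatment follows the CIPA result, so the planned prognostic evaluation by CIPA and by GLIM is distorted by treatment, in a direction that cannot be known in advance

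*Combined protocol and SAP*

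**What the plan says.** The secondary endpoints (Methods, The aims) include this one: "Evaluate prognostic variables (mortality, average stay, readmission rate) according to the two tools under study (CIPA vs. GLIM) at discharge", together with early readmissions and six-month mortality. The Workplan sets the follow-up: "Patients will be followed up during their hospital stay and 6 months after discharge".

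The Workplan also sets who is treated. For a positive CIPA: "All subjects with a positive test according to the CIPA instrument will be treated according to the usual protocol". For the discordant group: "while subjects with a negative CIPA test but a positive GLIM will be studied and constantly monitored, taking the appropriate measures according to criteria. optional". The Data Collect section says the same. The Background and Discussion present nutritional treatment as beneficial; the Discussion says that "early treatment can mitigate these deleterious effects".

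The variable table lists "Patients with nutritional treatment" as a follow-up item, so treatment is recorded. The statistical section describes the prognostic modelling this way: "For the follow-up study with CIPA positive patients, an initial univariate study of the factors that could determine prognostic levels". Its rule on confounding is general: "The existence of confusion will be evaluated by clinical criteria with a significant change of 10% over the coefficient obtained". It names no covariates and does not say how treatment received will enter. Neither the limitations section nor the limitations paragraph of the Discussion mentions treatment.

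**The concern.** One of the two classifications under evaluation decides who is routinely treated. If treatment works, as the protocol holds, a positive CIPA lowers the event rate in its own positive group. A weak association between CIPA and outcome could then mean a poor prognostic marker or a successful intervention, and the planned analysis cannot tell these apart. The GLIM contrast is altered too, because GLIM-positive patients are a mixture of routinely treated (CIPA-positive) and optionally treated (CIPA-negative) patients.

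There is also a mismatch of populations. An analysis confined to CIPA-positive patients has no CIPA-negative group, so it cannot evaluate prognosis by CIPA at all.

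The Discussion expects the study to help decide when the more complex and costly GLIM assessment is needed. A treatment-distorted prognostic contrast could mislead that decision.

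**Working it through.** The plan gives no figure to reproduce here: the sample of 490 has no stated derivation, and no event rates, treatment uptake or treatment effect are given. The calculation below illustrates direction only.

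**Inputs**
- From the documents: N = 490 (Workplan); GLIM prevalence 29.7% (the more recent Spanish survey in the Background); sensitivity 64% and specificity 82% against GLIM (the Discussion's figures for MUST, borrowed because none are given for CIPA).
- Assumed: untreated six-month mortality of 25% if both tests are positive, 15% in each discordant cell and 8% if both are negative; a treatment multiplier m on risk; a fraction q of CIPA-/GLIM+ patients treated.

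**Step 1. Cell sizes**
- CIPA+/GLIM+: 490 × 0.297 × 0.64 = 93.1
- CIPA-/GLIM+: 490 × 0.297 × 0.36 = 52.4
- CIPA+/GLIM-: 490 × 0.703 × 0.18 = 62.0
- CIPA-/GLIM-: 490 × 0.703 × 0.82 = 282.5

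**Step 2. No treatment effect**
- CIPA: positive (93.1 × 0.25 + 62.0 × 0.15)/155.1 = 0.210; negative (52.4 × 0.15 + 282.5 × 0.08)/334.9 = 0.0910; risk ratio 2.31.
- GLIM: positive (93.1 × 0.25 + 52.4 × 0.15)/145.5 = 0.214; negative (62.0 × 0.15 + 282.5 × 0.08)/344.5 = 0.0926; risk ratio 2.31.

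**Step 3. Equal benefit in all CIPA-positive patients, m = 0.75, q = 0**
- CIPA: 0.75 × 0.210 = 0.1575; 0.1575/0.0910 = 1.73.
- GLIM: (93.1 × 0.1875 + 52.4 × 0.15)/145.5 = 0.174; (62.0 × 0.1125 + 282.5 × 0.08)/344.5 = 0.0858; ratio 2.03.
- At m = 0.90 the ratios are 2.08 (CIPA) and 2.20 (GLIM); at m = 0.60, 1.39 and 1.83.

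**Step 4. Vary who benefits and who is treated, m = 0.75.** Risk in CIPA-/GLIM+ becomes 0.15 × [1 - q(1 - m)]. Where only GLIM-positive patients benefit, risk in CIPA+/GLIM- stays at 0.15.

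| Who benefits when treated | q | CIPA | GLIM |
|---|---|---|---|
| Everyone, equally | 0 | 1.73 | 2.03 |
| Everyone, equally | 0.5 | 1.79 | 1.95 |
| Everyone, equally | 1 | 1.85 | 1.87 |
| GLIM-positive only | 0 | 1.90 | 1.88 |
| GLIM-positive only | 0.5 | 1.96 | 1.81 |
| GLIM-positive only | 1 | 2.03 | 1.73 |

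Both tools fall below 2.31 in every row. Which falls further depends on two things the documents do not give.

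**Step 5. A second model.** Each positive test multiplies an assumed 6% base risk by 1.7, with four sensitivity/specificity pairs (56.7/69.0, 64/82, 47/76 and an assumed 80/80). The measure is the observed CIPA-to-GLIM ratio of risk ratios divided by its untreated value; below 1 is against CIPA. With equal benefit of 10-30% it runs from 0.77 to 0.998. With a 20% benefit in GLIM-positive patients only, it is 1.00-1.05 at q = 0 and 1.06-1.11 at q = 0.5. With no benefit it is 1.00.

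**Step 6. GLIM contrast within CIPA-positive patients.** With equal benefit, 0.25m/0.15m = 1.67 for any m. With benefit in GLIM-positive patients only, 0.25m/0.15 gives 1.50, 1.25 and 1.00 at m = 0.90, 0.75 and 0.60. For precision at m = 0.75 with equal benefit, expected deaths are 17.5 of 93.1 and 7.0 of 62.0. The standard error of the log ratio is √(1/17.5 - 1/93.1 + 1/7.0 - 1/62.0) = 0.417, so the 95% interval around 1.67 is about 0.74 to 3.77.

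**The case against.** A reader might infer that the comparison is biased against CIPA. The documents do not establish that. It requires roughly equal benefit in all treated patients and little treatment of CIPA-negative/GLIM-positive patients. The Background speaks of benefit in malnourished inpatients, and in this study GLIM defines malnutrition; nothing claims equal benefit in CIPA-positive/GLIM-negative patients. Treatment uptake in the CIPA-negative/GLIM-positive group is discretionary, so it is unknown rather than zero. This objection stands.

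It can also be said that the statistical section is generic rather than deficient: clinically relevant variables may enter the models, a 10% change-in-coefficient rule is given, and treatment is recorded. This stands only in part. The modelling is described for CIPA-positive patients, who all fall under the same treatment rule, so it cannot separate CIPA from the treatment it triggers.

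Nor does the plan announce a superiority test or a ranking of the tools on prognosis; it says only that prognosis will be evaluated according to both. That is fair, but putting the two sets of results side by side invites a ranking, and nothing in the plan warns against it.

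Finally, the GLIM contrast within CIPA-positive patients might be taken as a clean estimate of GLIM's added prognostic value. It is not: one treatment rule does not imply one treatment effect, and the interval is wide.

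**Conclusion.** The concern holds as a distortion of unknown direction and size. Routine treatment follows CIPA, the protocol considers it effective, no analysis step deals with it, and the described modelling population does not match the secondary objective. If benefit is about equal in everyone treated and few CIPA-negative/GLIM-positive patients are treated, the comparison is bent against CIPA. If nearly all of that group are treated, the gap almost closes; if benefit is confined to GLIM-positive patients, it vanishes or turns against GLIM; if treatment has no effect, there is no distortion. The mortality rates, treatment effect and uptake in the illustration are assumptions, and the accuracy figures are borrowed from another tool. The point concerns one secondary objective. The cross-sectional accuracy of CIPA against GLIM, the primary objective, is not affected.

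**What to change.** In the section on statistical analysis of the data:

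1. Extend the prognostic analysis to all followed patients, so that it matches the secondary objective.
2. Report mortality, stay and readmission with 95% confidence intervals in the four CIPA-by-GLIM cells, with the proportion given nutritional treatment in each.
3. Show GLIM-positive against GLIM-negative within CIPA-positive patients as a contrast under one treatment rule, stating that it is not free of treatment effect because benefit may differ by GLIM status. Report the same contrast within CIPA-negative patients separately, noting the optional measures.
4. Word all prognostic results as prognosis under CIPA-guided care, and do not rank the tools on prognosis.

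The cost is analysis and wording only, since the variables are already collected. The downside is small discordant cells (about 62 and 52 patients in the illustration) with wide intervals, and no head-to-head prognostic claim. No change to patient care is proposed.
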